4.3 Sample Size

[figure not shown]
The co-primary endpoints will be tested first for the combined high and standard adalimumab dose groups versus external placebo and then individual dose groups versus external placebo separately, controlling the familywise Type I error (multiple significance level) of 5% in a strong sense. For each individual test the nominal power will be calculated.

Assuming a 48% remission rate per PMS at Week 8 for the combined standard and high adalimumab induction dose groups and a remission rate per PMS of 19.83% for external placebo, a total of 77 subjects (presuming HD:SD = 46:31) in ITT-E population (see Section 5.1) provides at least 99% power for a one-sample two-sided Chi-square test using a significance level of 5%.

Assuming a 36% remission rate per Mayo Score at Week 52 for the combined standard and high maintenance dose groups and a remission rate per Mayo Score of 18.37% for external placebo, a total of 57 subjects (presuming HD:SD = 28:29) in the combined adalimumab maintenance dose groups in mITT-E population (see Section 5.1) provide 88% power for a one-sample two-sided Chi-square test using a significance level of 5%.

Assuming that the high adalimumab dose regimen is associated with higher efficacy than the standard adalimumab dose regimen and assuming a 52% remission rate per PMS at Week 8 for the high adalimumab induction dose group and a remission rate per PMS of 19.83% for external placebo, 46 subjects in the high adalimumab induction dose group of ITT-E population provide at least 99% power for a one-sample two-sided Chi-square test using a significance level of 4.95%.

Assuming a 41% remission rate per Mayo Score at Week 52 for the high adalimumab maintenance dose group and a remission rate per Mayo Score of 18.37% for external placebo, a total of 28 subjects in the high adalimumab maintenance dose group of the mITT-E population provide at least 80% power for a one-sample two-sided Chi-square test using a significance level of 4.95%.

Based on the assumption of a 75% response rate at Week 8, 93 subjects were to be included in the study (presuming 12 internal placebo subjects in the maintenance part of the study who were included prior to Amendment 4) to ensure 57 subjects in the combined adalimumab maintenance dose groups.

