13.0 References

Adalimum ab

M11-290 - Statistical Analysis Plan

Version 3.0 - 08 Aug 2019

Abbreviations

ADA Adalimumab

AE Adverse event

BMI Body mass index

CI Confidence Interval

CS Corticosteroid

CTC Common Toxicity Criteria

DB Double-blinded

DMARD Disease-modifying anti-rheumatic drug

DNA Deoxyribonucleic acid dsDNA Double-stranded DNA ECG Electrocardiogram every other week

ew every week

ESR Erythrocyte sedimentation rate

FMS Full mayo score

HACA Human anti-chimeric antibody hs-CRP High Sensitivity C-Reactive protein

IBD Inflammatory bowel disease

ICH International Conference on Harmonization
IDMC Independent Data Monitoring Committee

ITT Intent-to-treat

LOCF Last observation carried forward

MedDRA Medical Dictionary for Regulatory Activities

mITT Modified intent-to-treat

MTX Methotrexate

NRI Non-Responder imputation

NSAID Non-steroidal anti-inflammatory drug

OC Observed case
PK Pharmacokinetics
PMS Partial mayo score

PUCAI Pediatric Ulcerative Colitis Activity Index

RR Re-Randomized
SAE Serious adverse event
SAP Statistical analysis plan

SC Subcutaneous

Adalimumab M11-290 – Statistical Analysis Plan Version 3.0 – 08 Aug 2019

TB Tuberculosis

TNF Tumor necrosis factor UC Ulcerative Colitis

Addendum to Statistical Analysis Plan Version 3.0 (dated 08 August 2019)

Study M11-290

A Multicenter, Randomized, Double-Blind Study of the Human Anti-TNF Monoclonal Antibody Adalimumab in Pediatric Subjects with Moderate-to-Severe Ulcerative Colitis

Date: 03 March 2020

Introduction

This Addendum to the Statistical Analysis Plan Version 3.0 provides statistical details on additional sensitivity analyses as mentioned in Section 10.6 in the Statistical Analysis Plan.

Bayesian Sensitivity Analysis for the Second Co-Primary Endpoint

A Bayesian analysis as further described below was performed as sensitivity analysis for the primary analysis of the second co-primary endpoint (i.e., proportion of patients in clinical remission per Mayo score at Week 52 in Week 8 responders per partial Mayo score) of Study M11-290 (main, Ex-Japan) in order to take advantage of the number of N = 12 internal placebo patients and provide further insights into the difference in remission rates between Adalimumab and placebo taking into account prior anti-TNF experience status.

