Next, the posterior distribution on the difference (say, Delta) of the remission rates between Adalimumab and placebo was obtained from the respective posterior distributions of the remission rate in the placebo and Adalimumab groups, respectively using a convolution approach. Letting $x_1 \sim f_1(x)$ be the posterior density for the Adalimumab remission rates and $x_2 \sim f_2(x)$ the posterior density for the placebo remission rates, the difference $x \equiv x_1 - x_2$ is given by the following convolution: $f(x) = \int f_1(x) f_2(x-u) du = (f_1 * f_2)(x)$.

To take the prior anti-TNF experience status into account, this approach was applied separately for each stratum defined by the anti-TNF status (naïve and experienced) up to the point of obtaining the posterior distribution of Delta. After that the final posterior distribution of the difference in remission rates between Adalimumab and placebo was obtained by combining the two posterior distributions from anti-TNF experienced and naïve patients using the weights proportional to the sample sizes in the respective Adalimumab groups of Study M11-290.

As the final step, posterior probabilities for the difference in the remission rate (Delta) were evaluated for being greater than 0%, 10% and 15%. These posterior probabilities were evaluated for the combined dose groups ('M-HD/M-SD Combined'), the maintenance high dose group ('M-HD'), and the maintenance standard dose group ('M-SD').

Sensitivity analysis including robustification of priors

The additional analyses described below were performed as sensitivity analysis in order to further ensure the robustness of the main Bayesian approach described above. Here pooled data across anti-TNF experienced and naïve subjects from combined M-HD and M-SD doses was used. Considering the limited sample size in anti-TNF experienced subjects in Study M11-290, this pooled data approach seems to be the most appropriate to carry out a robust assessment of the main Bayesian analysis.

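### The Bayesian addendum's rule for combining the anti-TNF strata, read literally, gives a mixture of two posteriors instead of the posterior of the weighted-average difference, and it gives no formula to settle which was computed

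*SAP*

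**What the plan says.** The addendum describes a Bayesian analysis "performed as sensitivity analysis for the primary analysis of the second co-primary endpoint", which is Mayo remission at Week 52 in Week 8 responders. Its stated purpose is to use "the number of N = 12 internal placebo patients" and to take prior anti-TNF experience into account.

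Under the heading on the MAP prior approach there are three steps:

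1. Within a group, "the difference $x \equiv x_1 - x_2$ is given by the following convolution", and a formula is printed.
2. To bring in anti-TNF experience, "this approach was applied separately for each stratum defined by the anti-TNF status", up to the posterior of Delta.
3. The two stratum results are then merged into one final posterior for the remission difference. The rule is given in words only: "combining the two posterior distributions from anti-TNF experienced and naïve patients using the weights proportional to the sample sizes". The sizes meant are those of the adalimumab arms. This step has no formula, and no combined parameter is defined.

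The only outputs named are these: "posterior probabilities for the difference in the remission rate (Delta) were evaluated for being greater than 0%, 10% and 15" per cent, for the combined, M-HD and M-SD groups. No credible interval is specified. A later robustness check pools the strata, covers the combined doses only, and has no step that combines strata.

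**The concern.** The target that the addendum names is one trial-level quantity, the difference in remission rates. With two strata and sample-size weights that quantity is Delta = w_N·Delta_N + w_E·Delta_E, and its posterior is the distribution of the weighted sum.

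Weighting the two distributions gives something else: the distribution of the difference in a stratum picked at random with probabilities w_N and w_E. It adds the spread between strata and does not average the two uncertainties. Each reported probability then becomes a weighted mean of two stratum-specific probabilities.

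The addendum reports tail probabilities and nothing else, and these are what change between the two readings. This step is also where anti-TNF status enters the result.

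**Working it through.** **No figure to reproduce.** The addendum gives no posterior probability, stratum size, weight or prior parameter. The calculation can only show how far the two readings may differ under assumed inputs.

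**Formulas.** Let m and s be the mean and SD of a stratum posterior.

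- Mean, both readings: w_N·m_N + w_E·m_E
- Variance of the weighted sum: w_N²·s_N² + w_E²·s_E²
- Variance of the mixture: w_N·s_N² + w_E·s_E² + w_N·w_E·(m_N − m_E)²
- Tail of the mixture: P(Delta > c) = w_N·P(Delta_N > c) + w_E·P(Delta_E > c)

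**Inputs from the documents.** SAP section 4.3 plans 57 adalimumab subjects in maintenance. The protocol allows up to 25% anti-TNF experienced subjects. Taking the full 25% gives 57 × 0.25 = 14.25, so about 14 experienced and 43 naïve. There are 12 internal placebo patients. All rates and prior weights below are assumptions.

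**Scenarios.** Each is written naïve/experienced.

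In A to F every arm's posterior is a beta distribution with the stated mean and effective size.

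- A: adalimumab 36%/36%, placebo 18.37%/18.37%; sizes 43/14 and 60/30; w_N = 0.75
- B: 40%/24% and 18%/8%; sizes as A; w_N = 0.75
- C: rates as B; sizes 190/110 and 120/80; w_N = 0.75
- D: 40%/12% and 18%/8%; sizes as A; w_N = 0.75
- E: rates as A; sizes 43/14 and 15/8; w_N = 0.75
- F: rates as B; sizes 51/6 and 60/30; w_N = 0.90

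G and H add an informative adalimumab prior and the internal placebo patients, as the addendum does. The adalimumab data are 40% of 43 and 25% of 14. Placebo priors are centred on 16%/8% with the weight of 30/20 patients, plus 9/3 internal placebo patients remitting at those same rates. w_N = 43/57 = 0.754.

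- G: adalimumab priors centred on 35%/20%, weight 50/30
- H: adalimumab priors centred on 22%/10%, weight 100/50

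**Hand check, scenario B.** m = 0.220/0.160 and s = 0.089/0.121.

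- Weighted sum: 0.5625 × 0.00792 + 0.0625 × 0.01464 = 0.00537, SD 0.073
- Mixture: 0.75 × 0.00792 + 0.25 × 0.01464 + 0.1875 × 0.0036 = 0.01028, SD 0.101
- P(Delta > 10%) by mixture: 0.75 × 0.9117 + 0.25 × 0.6693 = 0.851. By weighted sum (simulated): 0.925

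**Results** (Monte Carlo, at least 1,000,000 draws; weighted sum → mixture):

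| | SD ratio | P(>0) | P(>10%) | P(>15%) |
|---|---|---|---|---|
| A | 1.39 | 0.992 → 0.958 | 0.847 → 0.779 | 0.636 → 0.603 |
| B | 1.38 | 0.998 → 0.976 | 0.925 → 0.851 | 0.773 → 0.714 |
| C | 1.43 | 1.000 → 1.000 | 0.995 → 0.964 | 0.917 → 0.834 |
| D | 1.69 | 0.994 → 0.905 | 0.855 → 0.743 | 0.636 → 0.620 |
| E | 1.36 | 0.951 → 0.900 | 0.782 → 0.733 | 0.621 → 0.602 |
| F | 1.26 | 0.997 → 0.979 | 0.929 → 0.889 | 0.796 → 0.764 |
| G | 1.39 | 0.998 → 0.983 | 0.933 → 0.866 | 0.770 → 0.711 |
| H | 1.35 | 0.957 → 0.908 | 0.513 → 0.514 | 0.176 → 0.253 |

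**Why H reverses.** The posterior means are 39.2/143 − 0.16 = 0.114 (naïve) and 8.5/64 − 0.08 = 0.053 (experienced). The combined mean is 0.754 × 0.114 + 0.246 × 0.053 = 0.099. The 10% threshold sits at the mean, so there is no gap. The 15% threshold lies above it, so the wider mixture has more mass beyond it. Zero lies below it, so the mixture has less.

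**The case against.** The strongest reply is that the addendum never says a mixture was used at this step. It uses mixture language where it means one: the placebo MAP prior is a mixture of betas, and the rMAP prior has an explicit mixing component. The step just before is a convolution, and the result is described as the posterior of a single difference. All of this fits a weighted sum.

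That stands as far as it goes: the text does not prove which was coded. It does not rescue the wording. The objects being weighted are the distributions, and the rMAP prior attaches weights to distributions in the same way to form a mixture. Without a formula, a second statistician following the sentence could produce either result.

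The second reply is that little hangs on it. This is a sensitivity analysis of one co-primary endpoint. The confirmatory test in SAP section 10.1 is a one-sample chi-square against a fixed rate. The pooled check yields the same three probabilities without any stratum combination. This also stands, except that the pooled check covers the combined doses only, so the M-HD and M-SD results have no such cross-check.

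A reader might go on to infer that this is the only analysis using the internal placebo arm. It is not. SAP section 5.1 keeps placebo as an mITT treatment group, section 10.1 reports binary endpoints by treatment group with 95% CIs, and the pooled Bayesian check uses the placebo data too.

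**Conclusion.** The point holds in this form: the combination rule as worded describes a mixture, which is not the posterior of the weighted-average difference, and the text leaves open which was computed. In the scenarios tried, P(Delta > c) under the mixture ranged from 11.2 points lower (D, 10% threshold: 0.855 to 0.743) to 7.7 points higher (H, 15% threshold: 0.176 to 0.253). The range rests entirely on assumed stratum sizes, rates and prior weights.

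Three stronger readings are tempting and are not supported. One is that the reported probabilities are wrong: the documents contain no results, so no output can be shown to be in error. Another is that a credible interval is wrong: none is specified. The last is that a mixture always understates the benefit of adalimumab: it does so when the threshold lies well below the posterior mean, but scenario H shows no gap at one threshold and a reversal at another.

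The step should be corrected, but its reach is limited to the stratified Bayesian sensitivity analysis.

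**What to change.** In the addendum, define Delta = w_N·Delta_N + w_E·Delta_E and state the weights for each of the combined, M-HD and M-SD comparisons. Draw Delta_N and Delta_E from their stratum posteriors, form the weighted sum draw by draw, and take P(Delta > 0%), P(Delta > 10%) and P(Delta > 15%) from those draws. State which rule was run and, if it was a mixture, recompute the three probabilities. Report the two stratum posteriors alongside, so that any difference between naïve and experienced subjects is visible in its own right.

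The cost is one sentence in the addendum and a few lines of R. No new data are needed, and no confirmatory result changes.

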The Meta-Analytic Predictive (MAP) prior approach

A Bayesian meta-analytic approach was used to leverage information from available historical studies to generate a meta-analytic predictive (MAP) prior1 for the probability of remission in the placebo group. In this approach a Bayesian hierarchical normal prior structure was used on the logit scale probabilities of the remission rates under the exchangeability assumption. The resulting MAP prior on the logit scale was then back transformed to the original probability scale and expressed as mixtures of beta densities using the expectation maximization algorithm (EM).² This MAP prior, expressed as mixture of beta densities, was then used to obtain the corresponding posterior distribution by using the data from the placebo group of the current Study M11-290. Historical data from studies GEMINI 1³ and OCTAVE Sustain⁴ were used as the only available placebo-controlled multi-center Phase III studies (comparing against active treatment with Vedolizumab and Tofacitinib respectively) in adult patients with moderately to severely active UC with similar subject population (i.e., failure or intolerance to prior

corticosteroids or IMMs), study design (i.e., randomized withdrawal), and endpoint definition (i.e., remission per Mayo score at 1 year).

For the derivation of an informative prior for the remission rate in the Adalimumab group, data in the Adalimumab group from historical Study M06-827 was used. This study was the only available placebo controlled multi-center study (comparing against active treatment with Adalimumab) in anti-TNF experienced and naïve adult UC patients, with induction and maintenance phase and efficacy measured based on Mayo score remission at Week 52. Of note, Study M06-826 only had a double-blind randomized induction period and could therefore not be included in this sensitivity analysis. However, Study M06-827 did not use a randomized withdrawal design, therefore respective data from the placebo group could not be considered in the evaluation of the informative prior for the placebo group in addition to GEMINI 1 and OCTAVE Sustain Studies. The posterior distribution for the Adalimumab group was then obtained by using the data from the Adalimumab group of current Study M11-290.

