First, the MAP prior for the remission rates in placebo was obtained on the pooled data in a similar way as described above and was represented as mixture of beta densities. Next, in order to investigate the robustness of the MAP prior against discounting (i.e., reducing the impact of the informative prior) this prior was 'robustified' using two different approaches: a) adding the Jeffreys' prior as a non-informative mixing component with a weight of alpha with the MAP prior of weight of (1-alpha), hereafter referred to as rMAP prior⁶ and b) applying a tuning parameter tau to scale the beta parameters of each one of the component beta densities of the MAP prior, hereafter referred to as eMAP prior.⁷ These priors (MAP, rMAP, eMAP) for the placebo rate were then used to obtain respective posterior distributions using the pooled data from the placebo group in the current Study M11-290. Similar approach was adopted for the Adalimumab group where we started from an informative beta prior distribution and applied the same alpha and tau values to obtain priors with reduced information and subsequently obtained the corresponding posterior distributions. Hereafter these posteriors for both placebo and the Adalimumab groups were referred to as MAP posterior, rMAP posterior and eMAP posterior.

As a final step, the posterior probabilities for the difference between Adalimumab and placebo groups were evaluated for being greater than 0%, 10% and 15% under three different scenarios: i) with no discounting (alpha = 0 or tau = 1), ii) from derived rMAP posteriors with alpha = 0.20, iii) derived eMAP posteriors with tau = 1.25. Note that a value of alpha = 0.2 for the rMAP prior represents a 20% discounting and similarly a value tau = 1.25 in eMAP reduces the parameters of each beta component density by 20%.

Empirical checking of Data and Prior Conflict

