To check if any obvious data-prior conflict was present in the analysis based on the MAP prior, an empirical approach was used by computing the marginal predictive probability of observing the currently observed responses in the placebo group using the above priors (rMAP, eMAP) for various values of alpha ($0 \le \text{alpha} < 1$) and tau (≥ 1). Note that for alpha = 0 the rMAP prior reduces to the MAP prior and similarly for tau = 1, eMAP prior becomes MAP prior. If there exists any obvious data-prior conflict which can be rectified by the rMAP or eMAP prior, then we would expect the marginal probability to increase for some choice of alpha > 0 (and tau > 1). A similar analysis was performed for the Adalimumab group.

Statistical Software

Analysis was implemented using R Studio (Version 1.1.453) and R statistical programming language (Version 3.5.1 64-bit) along with the following packages available on the Comprehensive R Archive Network (CRAN): "bayestestR," "Hmisc" and "RBesT." Outputs were generated using packages: "dplyr," "flextable," "purrr," "officer," "tibble" and "tidyr" available on CRAN.

References

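### The Bayesian addendum discounts the adult placebo prior by at most 20%, and its conflict check on 12 placebo children is too weak and unspecific to make up for that

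*SAP*

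**What the plan says.** The Addendum to SAP Version 3.0 (03 March 2020) describes its purpose as follows: "A Bayesian analysis as further described below was performed as sensitivity analysis for the primary analysis of the second co-primary endpoint". The aim is to "take advantage of the number of N = 12 internal placebo patients". The placebo prior is a meta-analytic predictive (MAP) prior built from GEMINI 1 and OCTAVE Sustain, studies "in adult patients with moderately to severely active UC". It models the "remission rates under the exchangeability assumption". The main Bayesian analysis is stratified by anti-TNF experience and applies no discount.

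The robustness section pools the anti-TNF strata and the two maintenance doses. The rMAP prior is formed by "adding the Jeffreys' prior as a non-informative mixing component with a weight of alpha"; the eMAP prior divides the beta parameters by tau. The adalimumab prior, from Study M06-827, is discounted with the same alpha and tau. The probabilities that the difference (Delta) exceeds 0%, 10% and 15% are then given for three scenarios: no discounting, "ii) from derived rMAP posteriors with alpha = 0.20, iii) derived eMAP posteriors with tau = 1.25".

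The section on empirical checking of data and prior conflict computes the marginal predictive probability of the observed placebo responses over alpha from 0 to just below 1 and tau from 1 upwards. If there is an obvious conflict that rMAP or eMAP can rectify, "then we would expect the marginal probability to increase for some choice of alpha > 0 (and tau > 1"). It gives no threshold, error rate or chance of detection.

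**The concern.** A robustness analysis of borrowed control data should show how the answer moves as the borrowing is withdrawn. Here the discount stops at 20%, so every reported probability sits at the end where the adult prior still carries most of the weight. A reader could see three similar numbers and conclude that the result does not depend on adult placebo data, although larger discounts were never shown.

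The conflict check is the only other protection. If it were sensitive and specific, a narrow discount range would matter less. With 12 children it is neither, so its outcome says little about whether adult and paediatric placebo rates are exchangeable.

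**Working it through.** **Inputs.** From the Addendum: 12 internal placebo patients, a Jeffreys Beta(0.5, 0.5) component with weight alpha, and reported settings alpha = 0, alpha = 0.20 and tau = 1.25. From SAP section 10.2: 18.37% is an upper 95% limit for adult placebo Week 52 remission, so the adult mean lies below it. The MAP parameters are not given. *Assumed:* a single beta prior with mean m of 10, 13, 15 or 18.37% and effective size s of 10, 20, 40, 100 or 300 (20 combinations).

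**The Addendum's own figure.** 1 - 0.20 = 0.80 and 1/1.25 = 0.80. The stated 20% discount reproduces for both settings. These are prior weights, before updating.

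**rMAP scan.** The marginal is (1 - alpha) x m_MAP(y) + alpha x m_Jeffreys(y), which is linear in alpha. It rises only if m_Jeffreys(y) > m_MAP(y), so scanning alpha asks one yes/no question. On the high side the answer is yes only from 4, 5 or 6 remitters of 12, depending on the prior. At a true rate of 30%, P(Y >= 4) = 0.507, P(Y >= 5) = 0.276 and P(Y >= 6) = 0.118. The scan therefore flags in 12-51% of trials.

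**eMAP scan.** For Beta(a/tau, b/tau), the marginal at 0/12 is the product over i = 0 to 11 of (b + i tau)/(a + b + i tau). Each factor with i >= 1 rises with tau, so 0/12 is flagged under any beta prior. On the high side the scan starts at 3, 4 or 5 of 12.

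**Either scan, exact binomial, n = 12:**

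| Situation | Flagged |
|---|---|
| True rate 30%, lowest combination (y >= 5 or y = 0) | 0.276 + 0.014 = 29% |
| True rate 30%, highest combination (y >= 3 or y = 0) | 0.747 + 0.014 = 76% |
| True rate equal to the prior mean (no conflict) | 14-49% |

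At a 13% mean and size 20 or more, the false-flag rate is 0.87^12 + P(Y >= 4) = 0.188 + 0.060 = 25%, mostly from 0/12. At the 18.37% mean with size 40 or more, 1/12 is flagged as well.

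**What a wider alpha range would show.** Illustration: adalimumab 21/57, placebo 4/12, placebo prior mean 13% and size 40, that is Beta(5.2, 34.8). Adalimumab has a Jeffreys prior to isolate the placebo prior; this is not the Addendum's own adalimumab prior. At y = 4, m_MAP = 0.0566 and m_Jeffreys = 0.0537, so rMAP does not flag. eMAP does: at tau = 1.25 the marginal is 0.0581. The posterior weight on the MAP component is w = (1 - alpha) x 0.0566 / [(1 - alpha) x 0.0566 + alpha x 0.0537]. Each probability is w times its alpha = 0 value plus (1 - w) times its alpha = 1 value.

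| alpha | w | P(Delta > 0) | P(Delta > 10%) |
|---|---|---|---|
| 0 | 1.00 | 0.99 | 0.87 |
| 0.2 | 0.81 | 0.91 | 0.77 |
| 0.5 | 0.51 | 0.79 | 0.60 |
| 0.8 | 0.21 | 0.67 | 0.43 |
| 1 (internal placebo only) | 0 | 0.58 | 0.31 |

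At tau = 1.25, P(Delta > 10%) is 0.84. The three reported settings give 0.77 to 0.87; the unreported part of the range runs down to 0.31.

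**The case against.** A stronger reading is tempting: that the check will usually miss a paediatric placebo rate about double the adult one, treats that as no conflict, and so leaves borrowing at 80-100%. The documents do not support it.

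- Both scans belong to the check. At a true 30%, one or the other flags in more than half of trials in 15 of the 20 assumed priors. At exactly twice the prior mean, about half of the priors exceed 50%. The 4/12 illustration is itself flagged by eMAP.
- The discounts are fixed scenarios, whatever the check shows. The 80% is a prior weight, and rMAP reweights with the data. With a prior mean of 14% and size 50, the posterior weight on the MAP component at alpha = 0.20 is 83% at 4/12, 64% at 5/12 and 34% at 6/12.
- The Addendum nowhere says that a non-increase shows agreement. It speaks only of obvious conflict that can be rectified. Exchangeability is weakly tested, not untested.

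It can also be said that unborrowed placebo data are already planned: SAP section 10.1 reports Week 52 endpoints by treatment group with 95% intervals, and section 5.1 lists the placebo group. The Addendum also gives a reason for pooling, namely the few anti-TNF-experienced subjects. Nor does the point reach the confirmatory one-sample test against 18.37%, which does not use the Addendum.

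All of this stands and limits the point. It does not remove it. A descriptive placebo rate does not show how the posterior probability of benefit changes as borrowing is withdrawn, and that is what a robustness analysis is for.

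**Conclusion.** The concern holds in a limited form. That the discount stops at 20%, that the rMAP scan is linear in alpha and that eMAP always flags 0/12 all follow from the Addendum without assumptions. The flag rates (12-51% for rMAP and 29-76% for either scan at a true 30%; 14-49% for either scan with no conflict) rest on the assumed single-beta priors, because the MAP prior is not printed. The posterior probabilities are one illustration and do not predict the trial's result. A flag is not specific to conflict, and the absence of a flag is weak reassurance. The consequence is confined to how much support the Bayesian sensitivity analysis can lend to co-primary 2.

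**What to change.** 1. In the robustness section, report P(Delta > 0%), P(Delta > 10%) and P(Delta > 15%) for the placebo prior at alpha = 0, 0.2, 0.5, 0.8 and 1, where 1 means internal placebo only. State which adalimumab prior is held alongside, since the Addendum discounts both arms together. Name the probability regarded as supportive and the alpha at which the conclusion changes.
2. In the conflict section, state that with 12 patients the absence of a rise is not evidence of exchangeability, and do not cite it as such.
3. Do not replace the check with a prior-predictive tail test. At a one-sided 5% level such a test detects a true 30% less often than the existing check under all 20 assumed priors (for example 28% against 52% at mean 13%, size 20-300). Its false-flag rate would be lower, but the sample is too small for either to settle the question.

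The cost is a few more runs of existing R code, which already scans alpha up to just below 1, and a short wording change. No new data are needed. The downside is that the probabilities of benefit may look less favourable at larger alpha.
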